14.2. Laboratory Safety Assessments

The following laboratory assessments will be performed to evaluate the safety profile of BIIB054:

- Hematology: Complete blood count with differential and platelet count, INR, PT, and APTT
- Blood chemistry: total protein, albumin, creatinine, blood urea nitrogen, uric acid, bilirubin (total and direct), alkaline phosphatase, alanine aminotransferase, aspartate aminotransferase, gamma-glutamyl transferase, glucose, calcium, phosphorus, bicarbonate, chloride, sodium, and potassium
- Urinalysis: dipstick for blood, protein, and glucose (microscopic examination may also be performed)

CONFIDENTIAL

The information contained herein may not be used, disclosed, or published without the written consent of Biogen MA Inc.

14.3. Immunogenicity Assessments

The following assessments will be performed to determine the safety of BIIB054:

- Collection and analysis of serum samples for the presence and titer of anti-BIIB054 antibodies

CONFIDENTIAL

The information contained herein may not be used, disclosed, or published without the written consent of Biogen MA Inc.

15. SAFETY DEFINITIONS, RECORDING, REPORTING, AND RESPONSIBILITIES

Throughout the course of the study, every effort must be made to remain alert to possible AEs. If an AE occurs, the first concern should be for the safety of the subject. If necessary, appropriate medical intervention should be provided.

At the signing of the main ICF, each subject must be given the names and telephone numbers of study site staff for reporting AEs and medical emergencies.

15.1. Definitions

15.1.1. Adverse Event

An AE is any untoward medical occurrence in a patient or clinical investigation subject administered a pharmaceutical product and that does not necessarily have a causal relationship with this treatment. An AE can therefore be any unfavorable and unintended sign (including an abnormal laboratory finding), symptom, or disease temporally associated with the use of a medicinal (investigational) product, whether or not related to the medicinal (investigational) product.

Determination of whether an abnormal laboratory value, vital sign result, MRI result, physical/neurological examination finding, and/or ECG result meet the definition of an AE will be made by the Investigator. Abnormal results are not considered AEs unless 1 or more of the following criteria are met:

- The result meets the criteria for an SAE.
- The result requires the subject to receive specific corrective therapy.
- The result is considered by the Investigator to be clinically significant.

15.1.2. Serious Adverse Event

An SAE is any untoward medical occurrence that at any dose:

- Results in death
- In the view of the Investigator, places the subject at immediate risk of death (a life-threatening event); however, this does not include an event that, had it occurred in a more severe form, might have caused death
- Requires inpatient hospitalization or prolongation of existing hospitalization
- Results in persistent or significant disability/incapacity

CONFIDENTIAL

The information contained herein may not be used, disclosed, or published without the written consent of Biogen MA Inc.

- Results in a congenital anomaly/birth defect
- Is a medically important event

A medically important event is an AE that, in the opinion of the Investigator, may jeopardize the subject or may require intervention to prevent one of the other outcomes listed in the definition above. (Examples of such medical events include allergic bronchospasm requiring intensive treatment in an emergency room or convulsions occurring at home that do not require an inpatient hospitalization.)

15.1.3. Prescheduled or Elective Procedures or Routinely Scheduled Treatments

A prescheduled or elective procedure or a routinely scheduled treatment will not be considered an SAE, even if the subject is hospitalized. The study site must document all of the following:

- The prescheduled or elective procedure or routinely scheduled treatment was scheduled (or was on a waiting list to be scheduled) prior to obtaining the subject's consent to participate in the study.
- The condition requiring the prescheduled or elective procedure or routinely scheduled treatment was present before and did not worsen or progress in the opinion of the Investigator between the subject's consent to participate in the study and the time of the procedure or treatment.
- The prescheduled or elective procedure or routinely scheduled treatment is the sole reason for the intervention or hospital admission.
 - If a subject is hospitalized due to local requirements for administration of the study treatment, the hospitalization should not be considered an SAE unless one of the requirements in Section 15.1.2 is met.

15.2. Safety Classifications

15.2.1. Investigator Assessment of Events

All events must be assessed to determine the following:

- If the event meets the criteria for an SAE as defined in Section 15.1.2.
- The relationship of the event to study treatment, to the LP procedure, and to the DaTscan (ioflupane I123 Injection) radioligand (hereafter referred to as the radioligand), as defined in Section 15.2.2.
- The severity of the event as defined in Section 15.2.3.

CONFIDENTIAL

The information contained herein may not be used, disclosed, or published without the written consent of
Biogen MA Inc.

15.2.2. Relationship of Events to Study Treatment, to the Lumbar Puncture Procedure, and to the Radioligand

The following definitions should be considered when evaluating the relationship of AEs and SAEs to the study treatment, to the LP procedure, and to the radioligand.

Relationship of Event to Study Treatment	
Not related	An AE will be considered “not related” to the use of the investigational product if there is not a reasonable possibility that the event has been caused by the product under investigation. Factors pointing toward this assessment include but are not limited to: the lack of reasonable temporal relationship between administration of the investigational product and the AE, the presence of a biologically implausible relationship between the product and the AE, or the presence of a more likely alternative explanation for the AE.
Related	An AE will be considered “related” to the use of the investigational product if there is a reasonable possibility that the event may have been caused by the product under investigation. Factors that point toward this assessment include but are not limited to: a positive rechallenge, a reasonable temporal sequence between administration of the investigational product and the AE, a known response pattern of the suspected product, improvement following discontinuation or dose reduction, a biologically plausible relationship between the product and the AE, or a lack of an alternative explanation for the AE.
Relationship of Event to LP	
Not related	An AE will be considered “not related” to the LP procedure if there is not a reasonable possibility that the event has been caused by the LP procedure. Factors pointing toward this assessment include but are not limited to: the lack of reasonable temporal relationship between the LP procedure and the AE, the presence of a biologically implausible relationship between the LP procedure and the AE, or the presence of a more likely alternative explanation for the AE.
Related	An AE will be considered “related” to the LP procedure if there is a reasonable possibility that the event may have been caused by the LP procedure. Factors that point toward this assessment include but are not limited to: a reasonable temporal sequence between the LP procedure and the AE, a known response pattern of the LP procedure (e.g., bleeding from the puncture site), a biologically plausible relationship between the LP procedure and the AE, or a lack of an alternative explanation for the AE.
Relationship of Event to Radioligand	
Not related	An AE will be considered “not related” to the use of the radioligand if there is not a reasonable possibility that the event has been caused by the radioligand. Factors pointing toward this assessment include but are not limited to: the lack of reasonable temporal relationship between administration of the radioligand and the AE, the presence of a biologically implausible relationship between the radioligand and the AE, or the presence of a more likely alternative explanation for the AE.

CONFIDENTIAL

The information contained herein may not be used, disclosed, or published without the written consent of Biogen MA Inc.

Related	An AE will be considered “related” to the use of the radioligand if there is a reasonable possibility that the event may have been caused by the radioligand. Factors that point toward this assessment include but are not limited to: a positive rechallenge, a reasonable temporal sequence between administration of the radioligand and the AE, a known response pattern of the suspected radioligand, improvement following discontinuation or dose reduction, a biologically plausible relationship between the radioligand and the AE, or a lack of an alternative explanation for the AE.
---------	----------------------------------------------------------------------------------------------------------------------------------------------------------------------------------------------------------------------------------------------------------------------------------------------------------------------------------------------------------------------------------------------------------------------------------------------------------------------------------------------------------------------------------------------------------------------------------------------------

15.2.3. Severity of Events

The severity of AEs and SAEs will be graded using the National Cancer Institute Common Terminology Criteria for Adverse Events (CTCAE), version 5.0. Any AE not listed in the CTCAE will be graded as follows:

Severity of Event	
Grade	Definition
1	Mild AE (asymptomatic or mild symptoms; clinical or diagnostic observations only; intervention not indicated)
2	Moderate AE (minimal, local, or noninvasive intervention indicated; limiting age-appropriate instrumental ADLs)
3	Severe or medically significant AE (not immediately life-threatening; hospitalization or prolongation of hospitalization indicated; disabling; limiting self-care ADLs)
4	Life-threatening AE (urgent intervention indicated)
5	Death related to AE

15.2.4. Expectedness of Events

Expectedness of all AEs will be determined by Biogen according to the Investigator's Brochure.

15.3. Monitoring and Recording Events

15.3.1. Adverse Events

Any AE (including SAEs) experienced by the subject between the time of first dose of study treatment and the Final Visit is to be recorded on the eCRF, regardless of the severity of the event, its relationship to study treatment, its relationship to the LP procedure, or its relationship to the radioligand. Nonserious AEs that occur during the Screening period and that are assessed by the Investigator as related to the ligand will be captured by the sites on the AE eCRF. At each study visit, the Investigator will assess the subject for AEs and will record any new AEs or updates to previously reported AEs on the eCRF.

AEs that are ongoing when the subject completes or discontinues the study will be followed by the Investigator until the event has resolved, stabilized, or returned to baseline status. AE outcome will be recorded on the eCRF, as applicable.

CONFIDENTIAL

The information contained herein may not be used, disclosed, or published without the written consent of Biogen MA Inc.

15.3.2. Serious Adverse Events

Any SAE experienced by the subject between the time of the signing of the main ICF and the Final Visit is to be recorded on an SAE form, regardless of the severity of the event, its relationship to study treatment, its relationship to the LP procedure, or its relationship to the radioligand. SAEs must be reported to Biogen within 24 hours as described in Section 15.3.3.

Follow-up information regarding an SAE also must be reported within 24 hours. Subjects will be followed for all SAEs until the Final Visit. Thereafter, an SAE should be reported to Biogen only if the Investigator considers it to be related to study treatment.

Any SAE that is ongoing when the subject completes or discontinues the study will be followed by the Investigator until the event has resolved, stabilized, or returned to baseline status.

15.3.3. Immediate Reporting of Serious Adverse Events

In order to adhere to all applicable laws and regulations for reporting an SAE, the study site must formally notify Biogen within 24 hours of the study site staff becoming aware of the SAE. It is the Investigator's responsibility to ensure that the SAE reporting information and procedures are used and followed appropriately.

Reporting Information for SAEs

Any SAE that occurs between the time that the subject has signed the main ICF and the Final Visit must be reported to Biogen within 24 hours of the study site staff becoming aware of the event. After the Final Visit, the event should be reported only if the Investigator considers it related to study treatment.

A report ***must be submitted*** to Biogen regardless of the following:

- Whether or not the subject has undergone study-related procedures
- Whether or not the subject has received study treatment
- The severity of the event
- The relationship of the event to study treatment, to the LP procedure, or to the radioligand

To report initial or follow-up information on an SAE, fax a completed SAE form; refer to the Study Reference Manual for complete contact information.

15.3.3.1. Deaths

Death is an outcome of an event. The event that resulted in death should be recorded on the appropriate eCRF. All causes of death must be reported as SAEs within 24 hours of the site becoming aware of the event. The Investigator should make every effort to obtain and send

CONFIDENTIAL

The information contained herein may not be used, disclosed, or published without the written consent of Biogen MA Inc.

death certificates and autopsy reports to Biogen. The term death should be reported as an SAE only if the cause of death is not known and cannot be determined.

15.3.4. Suspected Unexpected Serious Adverse Reactions

Suspected unexpected serious adverse reactions (SUSARs) are SAEs that are unexpected and judged by the Investigator or Biogen to be related to the study treatment administered.

Appropriate personnel at Biogen will unblind SUSARs for the purpose of regulatory reporting. Biogen will submit SUSARs (in blinded or unblinded fashion) to regulatory agencies according to local law. Biogen will submit SUSARs to Investigators in a blinded fashion.

15.4. Procedures for Handling Special Situations

15.4.1. Pregnancy

Subjects should not become pregnant or impregnate their partners during the study and for 6 months after their last dose of study treatment. If a female subject becomes pregnant, study treatment must be discontinued *immediately*.

The Investigator must report a pregnancy occurring in a female subject from first dose of study treatment up to 6 months after the last dose, by faxing the appropriate form to Biogen within 24 hours of the study site staff becoming aware of the pregnancy; refer to the Study Reference Manual for complete contact information. The Investigator or study site staff must report the outcome of the pregnancy to Biogen. A pregnancy is not considered an AE and should not be recorded on the AE eCRF.

Congenital abnormalities and birth defects in the offspring of male or female subjects should be reported as an SAE if conception occurred during the study treatment period.

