7. Score of ≤ 2.5 on the Modified Hoehn and Yahr Scale.
8. Screening DaT/SPECT results demonstrating activity in the striatum is either asymmetric, absent in the putamen and/or one or both caudate nuclei, consistent with neurodegenerative Parkinsonism, as assessed with qualitative, visual assessment. DaT/SPECT images will be reviewed by a central reader to confirm eligibility.
9. All women of childbearing potential and all men must practice highly effective contraception during the study and for 6 months after their last dose of study treatment. For further details of contraceptive requirements for this study, please refer to Section 15.5.

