15.5. Contraception Requirements

All women of childbearing potential and all men must practice highly effective contraception during the study and for 6 months after their last dose of study treatment. In addition, male subjects should not donate sperm for the duration of the study and for at least 6 months after their last dose of study treatment.

For the purposes of this study, women who do not meet one of the following criteria listed below are considered to be physiologically capable of becoming pregnant and are, therefore, defined as women of childbearing potential:

- Postmenopausal
 - 12 continuous months of natural (spontaneous) amenorrhea without an alternative medical cause and a serum follicle stimulating hormone level >40 mIU/mL
 - 6 weeks after surgical bilateral oophorectomy with or without hysterectomy
- Posthysterectomy
- Female surgical sterilization (e.g., bilateral tubal ligation)

For the purposes of the study, highly effective contraception is defined as use of 1 of the following:

For female subjects:

- Established use of oral, intravaginal, or transdermal combined (estrogen and progestogen containing) hormonal methods of contraception associated with the inhibition of ovulation.
- Established use of oral, injected, or implanted progestogen-only hormonal methods of contraception.
- Placement of an intrauterine device or intrauterine hormone-releasing system.

CONFIDENTIAL

The information contained herein may not be used, disclosed, or published without the written consent of Biogen MA Inc.

- Bilateral tubal occlusion.
- Sex with a male partner who has undergone surgical sterilization (with the appropriate postvasectomy documentation of the absence of sperm in the ejaculate).

For male subjects:

- A vasectomy with subsequent negative semen analysis.
- Sex with a woman who uses the methods described for female subjects if she is of childbearing potential.

True abstinence, when this is consistent with the preferred and usual lifestyle of the subject, can be considered an acceptable method of contraception based on the evaluation of the Investigator who should also take into consideration the duration of the clinical trial. Periodic abstinence (e.g., calendar, ovulation, symptothermal, postovulation methods) and withdrawal are not considered acceptable methods of contraception.

Pregnancy reporting is described in Section [15.4.1](#).

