15.6. Safety Responsibilities

15.6.1. The Investigator

The Investigator's responsibilities include the following:

- Monitor and record all AEs, including SAEs, on the eCRF regardless of the severity, relationship to study treatment, relationship to the LP procedure, or relationship to the radioligand.
- Determine the seriousness, relationship to study treatment, relationship to the LP procedure, relationship to the radioligand, and severity of each event.
- Determine the onset and resolution dates of each event.
- Monitor and record all pregnancies in female subjects and follow up on the outcome of all pregnancies.
- Complete an SAE form for each SAE and fax it to Biogen within 24 hours of the study site staff becoming aware of the event.
- Pursue SAE follow-up information actively and persistently. Follow-up information must be reported to Biogen within 24 hours of the study site staff becoming aware of new information.
- Ensure all AE and SAE reports are supported by documentation in the subjects' medical records.

CONFIDENTIAL

The information contained herein may not be used, disclosed, or published without the written consent of
Biogen MA Inc.

- Pursue AE follow-up information, if possible, until the event has resolved or become stable. Record AE follow-up information, including resolution, on the eCRF, as applicable.
- Report SAEs to local ethics committees, as required by local law.

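### The birth-defect SAE rule in Section 15.4.1 covers a shorter, undefined conception window than the 6 months the protocol uses elsewhere, and partner pregnancies have no required report

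*Protocol*

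**What the plan says.** Several parts of the protocol set a window for conception, and they do not all use the same one.

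- **Contraception and avoidance, both sexes.** Inclusion criterion 9 (Section 8.1) states: "All women of childbearing potential and all men must practice highly effective contraception during the study and for 6 months after their last dose". Section 15.4.1 adds: "Subjects should not become pregnant or impregnate their partners during the study and for 6 months after their last dose of study treatment". Section 15.5 adds that "male subjects should not donate sperm for the duration of the study and for at least 6 months after their last dose of study treatment".
- **Pregnancy reporting, women only.** Section 15.4.1: "The Investigator must report a pregnancy occurring in a female subject from first dose of study treatment up to 6 months after the last dose". The same paragraph requires the pregnancy outcome to be sent to the sponsor. Section 15.6.1 lists the matching investigator duty: "Monitor and record all pregnancies in female subjects and follow up on the outcome of all pregnancies".
- **Birth defects, both sexes.** Section 15.4.1 covers congenital abnormalities in "offspring of male or female subjects should be reported as an SAE if conception occurred during the study treatment period".
- **General SAE rules.** Section 15.1.2 counts a congenital anomaly or birth defect as an SAE criterion and sets no limit on when conception took place. On events after the Final Visit, Section 15.3.2 says: "Thereafter, an SAE should be reported to Biogen only if the Investigator considers it to be related to study treatment". Section 15.3.3 repeats that limit.

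**The concern.** The birth-defect sentence is narrower in time than the sentences around it. The protocol asks men and women to avoid conception for 6 months after the last dose, and asks sites to report women's pregnancies over that time. Yet it ties the SAE status of a malformation to the treatment period, a term Section 15.4.1 does not define.

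The sentence also covers the offspring of male subjects, but no other rule requires a site to report or follow a pregnancy in a male subject's partner. A site could meet every pregnancy duty and have no pregnancy record from which a defect in a man's child would come to light.

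What is at stake is the consistency of safety reporting: whether a malformation is handled as an SAE, with 24-hour notification under Section 15.3.3 and possible SUSAR assessment under Section 15.3.4, and whether it reaches the sponsor at all when the subject is the father.

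**Working it through.** The plan gives no figure of its own here, so there is none to reproduce. The check sets the rules side by side and then sizes the gap.

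**Coverage by case**

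| Conception | Pregnancy and outcome report required? | Defect an SAE under 15.4.1? |
|---|---|---|
| Female subject, on treatment | Yes (15.4.1, 15.6.1) | Yes |
| Female subject, within 6 months after last dose | Yes (15.4.1, 15.6.1) | No |
| Male subject's partner, on treatment | No | Yes |
| Male subject's partner, within 6 months after last dose | No | No |

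Row 2 is where Section 15.1.2, read alone, points to an SAE and Section 15.4.1, read alone, does not. Row 3 is an SAE rule with no pregnancy report to feed it. Row 4 has no dedicated route at all.

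**Length of the gap**

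Inputs: 6 months taken as 26 weeks; longest treatment 48 + 112 = 160 weeks (Section 7.2); last dose at Week 96 for subjects who do not continue (Section 7.2.3.3); Final Visit 12 weeks after the last dose (Section 7.2.3.3).

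Share of the conception window that falls after the last dose = 26 / (weeks from first to last dose + 26):

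- Last dose at Week 160: 26/186 = 14%
- Last dose at Week 96: 26/122 = 21%
- Treatment stopped at Week 48: 26/74 = 35%
- Treatment stopped at Week 24: 26/50 = 52%

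If the undefined treatment period is taken to run one 4-week dosing interval past the last dose, the uncovered part is 26 − 4 = 22 weeks. The shares become 22/186 = 12%, 22/122 = 18%, 22/74 = 30% and 22/50 = 44%.

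These are shares of time, not of conceptions. The documents give no count of men, of women of childbearing potential or of expected pregnancies, so no share of conceptions can be computed.

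**Position of the Final Visit**

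Of the 26 weeks, 26 − 12 = 14 fall after the Final Visit, with no scheduled contact. A birth following conception after the last dose would come after that visit. Births from late on-treatment conceptions would too: assuming about 38 weeks from conception to birth (a figure not in the documents), conceptions in roughly the last 38 − 12 = 26 weeks of treatment lead to births after the Final Visit. Each week of difference in that assumption moves the result by one week. So an extended birth-defect rule operates largely in the period where Sections 15.3.2 and 15.3.3 ask only for related SAEs.

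**The case against.** The strongest reply is that the information is mostly not lost. Every pregnancy in a female subject must be reported through 6 months after the last dose, with its outcome, and a malformation is an outcome. For women, what may be lost is SAE classification and its clock, not the fact itself. This stands. A reader might infer that a site following the rules would leave a malformation after a post-treatment conception unreported; for women the outcome duty rules that out.

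A reader might also infer that most exposed conceptions escape capture. The documents do not support that. By time the uncovered part is a minority for any planned course. The inference could hold only if partner pregnancies dominated, for which there is no figure. The male-to-female ratio in Section 5.1 describes the disease in western populations, not this trial's enrolment.

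A third tempting reading is that Section 15.3.2 overrides Section 15.4.1 once the Final Visit has passed. Section 15.4.1 is the specific rule, placed under special situations, with no cut-off on the date of birth. It is naturally read as prevailing over the general limit. An SAE judged related also stays reportable after the Final Visit. An express sentence would remove doubt, but the present text is not a flat contradiction on this point.

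Finally, few pregnancies are expected at ages 40 to 80, and a partner-consent form is a new document needing ethics approval. Both points are fair, and they limit the importance of the finding. Neither explains why the birth-defect sentence uses a different window from the rest of its own section.

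**Conclusion.** The concern holds as a mismatch in safety-reporting rules. The birth-defect SAE rule stops at an undefined end of treatment, while the protocol's own window for both sexes runs about 26 weeks beyond the last dose. That is 14% of the conception window for a last dose at Week 160 and 21% at Week 96, or 12% and 18% if treatment is deemed to last 4 weeks past the final infusion.

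For women the consequence is uncertain SAE status. For men it is a real gap: a defect in a child conceived after the last dose has no dedicated rule, and a partner's pregnancy has no required report at any time. The number of events affected cannot be computed and is expected to be small. No endpoint, sample size, power or efficacy analysis is affected. The conclusion rests on the protocol text and on taking 6 months as 26 weeks.

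**What to change.** 1. In Section 15.4.1, define the birth-defect SAE rule by conception from the first dose to 6 months after the last dose, for offspring of male and female subjects alike. This reuses the window the sponsor already applies to women's pregnancies.
2. In the same place, state that the rule applies regardless of the Final Visit limit in Sections 15.3.2 and 15.3.3.
3. Reconcile Sections 15.4.1 and 15.6.1 so that a partner pregnancy a site learns of within that window is reported and its outcome followed, with the partner's consent.

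Items 1 and 2 are amendment wording only, with no added visit, assessment or analysis. Item 3 costs more: a partner-consent form needing ethics approval across about 85 planned sites, in a trial that Version 8 records as already enrolled at 357 subjects. The follow-up workload should be very small. Item 3 is secondary, and items 1 and 2 can proceed without it.
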